8.2.3 Correlative Studies for Research/Pharmacokinetic Studies

Not applicable

8.2.4 Samples for Genetic/Genomic Analysis

8.2.4.1 Description of the scope of genetic/genomic analysis

Not applicable, genetic/genomic analysis will not be performed in this study.

8.2.4.2 Description of how privacy and confidentiality of medical information/biological specimens will be maximized

All subject data in this clinical trial will be anonymized using the same system, each subject's identity will remain anonymous in the clinical trial database.

The clinical trial database, which may be shared with appropriate regulatory agencies, in addition to access from the pharmaceutical collaborators and investigators, will contain clinical/demographic data on subject's age, ethnicity, sex, diagnosis, treatment, response to treatment, adverse events as per the standards of human clinical research, however, all the data will be anonymized without any link to individual identifying information.

8.2.4.3 Management of Results

The results of all clinical documentation and laboratory data performed at the NIH Clinical Center will be available to subjects through the NIH online patient portal and through NIH medical records on request. Clinical documentation and laboratory data will be shared with subjects' home clinicians on request. Subjects will be encouraged to inform their home clinicians about participation in the study, and the Investigators will maintain close communication with home clinicians regarding any clinically relevant issues.

8.2.4.4 Genetic counseling

Not applicable, genetic counseling will not be performed in this study.

8.3 Safety and Other Assessments

8.3.1 Physical Examination

At the times detailed in the Section **1.3, Schedule of Activities (SoA)**, subjects will undergo a complete physical examination (PE), which is to be completed by a physician or an appropriately trained health professional. Any abnormal physical examination finding that is deemed clinically important (i.e., is associated with symptoms and/or requires medical intervention) and is changed from baseline will be recorded as an AE as described in Section **8.4**.

8.3.2 Vital Signs

Vital signs will be assessed in accordance with times and details indicated in the Section **1.3, Schedule of Activities (SoA)**. Any abnormal vital sign that is deemed clinically significant (i.e.,

is associated with symptoms and/or requires medical intervention) will be recorded as an AE as described in Section **8.4**.

8.3.3 Clinical Laboratory Determinations

Blood and urine samples for clinical laboratory tests will be collected at the times detailed in the Section **1.3, Schedule of Activities (SoA)**. Samples will be collected for evaluation of anti-burosomab antibodies at NIH visits according to the Section **1.3, Schedule of Activities (SoA)**. Samples will be sent to BioAgilytix Labs, LLC and Toray Research Center, Inc, specialty lab services that have been previously contracted by Kyowa Kirin to evaluate for the development of anti-burosomab antibodies, burosomab concentration, and neutralizing antibodies, respectively. At any time during the study, abnormal laboratory parameters which are clinically relevant (e.g., require dose interruption of study treatment, lead to clinical symptoms or signs, or require therapeutic intervention), whether specifically requested in the protocol or not, will be recorded on the Adverse Events eCRF page and defined according to the Common Terminology Criteria for Adverse Events (CTCAE) Version 5.0.

Samples will be collected, processed, and stored according to the instructions provided in the Laboratory Manual.

The investigator or qualified sub-investigator will review all laboratory results for clinical significance. Any laboratory result deemed clinically significant (i.e., is associated with signs and symptoms and/or requires medical intervention) will be recorded as an AE as described in Section **8.4**.

8.3.4 ¹⁸F-sodium fluoride PET/CT bone scan

Because FD is a benign neoplastic process, ¹⁸F-NaF PET/CT scans will be performed at NIH visits on Weeks 0 and 48 to evaluate for any potential deleterious effects of burosomab on FD lesion activity. Subjects will receive intravenous ¹⁸F-Sodium Fluoride via a placed catheter. Images will be obtained 1 hour after injection and will last approximately 1 ½ hours. Only subjects who can hold still without requiring sedation will undergo scanning.

8.3.5 Renal Ultrasound

Renal ultrasounds to assess for nephrocalcinosis will be performed at NIH visits on Weeks 0 and 48.

8.3.6 Skeletal Survey

Plain film x-rays of the arms, legs, pelvis, ribs, and lateral spine will be obtained at Weeks 0 and 48 to evaluate for the development or progression of skeletal deformities, and to assess for rachitic metaphyseal changes in growing children.

8.3.7 Bone Biopsy

Percutaneous core needle bone biopsies will be performed in adult subjects with capacity to consent at Weeks 0 and 48. Because FD is a benign neoplastic process, biopsies will be performed to evaluate for any potential deleterious effects of burosomab on FD tissue. This will include evaluation of tissue histology for changes in cell proliferation and neoplastic bone content. The first biopsy will be performed prior to burosomab therapy (baseline) and the second at the same site following completion of therapy (post treatment). The biopsies will be performed

by a licensed, credentialed practitioner in Interventional Radiology or the operating room of the NIH Clinical Center under local anesthesia with sedation. The biopsies will be performed from areas containing FD. The PI and the surgeon will jointly determine which sites are to be biopsied. All subjects will be evaluated by an anesthesiologist, who will determine the level of anesthesia needed based on clinical evaluation of the patient and planned procedure. Only biopsies judged to be minimally invasive (i.e. percutaneous procedures that allow bone to be removed via a core needle) will be performed. A bone biopsy will not be done if there is no site containing FD that allows a minimally invasive procedure with minimal risk of fracture.

8.4 Adverse Events and Serious Adverse Events

8.4.1 Definition of Adverse Event

An adverse event (AE) is defined as any untoward medical occurrence associated with the use of a drug in humans, whether or not considered drug related (21 CFR 312.32 (a)). An AE can therefore be any unfavorable and unintended sign (including an abnormal laboratory finding, for example), symptom, or disease temporally associated with the use of a medicinal (investigational) product, whether or not related to the medicinal (investigational) products.

Pre-existing diseases or conditions will not be considered AEs unless there is an increase in the frequency or severity, or a change in the quality, of the disease or condition. Worsening of a pre-existing condition is considered an AE.

Any abnormal laboratory test results (hematology, clinical chemistry, or urine) or other safety assessments (e.g., vital sign measurements), including those that worsen from Screening/baseline that are felt to be clinically significant in the medical and scientific judgment of the Investigator are to be recorded as AEs. Elective surgeries to correct or prevent skeletal deformities are considered standard treatment for FD [19], and will not be reported as AE's. These events will be recorded as part of the medical history at each NIH visit, according to the Schedule of Activities.

8.4.2 Definition of Serious Adverse Events (SAE)

A serious adverse event (SAE) is an AE that meets any of the following criteria in the view of either the Investigator, Ultragenyx, or Kyowa Kirin:

- Death
- Life-threatening
 - A life-threatening AE is an event that places the patient or subject at immediate risk of death. It does not include events that if it had occurred in a more serious or severe form might have caused death. For example, drug induced hepatitis that resolved without evidence of hepatic failure would not be considered life threatening even though drug induced hepatitis can be fatal.
- Inpatient hospitalization or prolongation of existing hospitalization
 - Hospitalization is defined as a full admission to hospital for a period of 24 hours or longer for diagnosis and treatment. This includes prolongation of an existing inpatient hospitalization. Examples of visits to a hospital facility that do not meet the serious criteria for hospitalization include:

- Emergency room visits (that do not result in a full hospital admission)
- Preplanned or elective procedures prior to study enrollment (e.g., outpatient surgery)
- Protocol procedures
- Hospitalization signifies that the subject has been detained (usually involving at least an overnight stay) at the hospital or emergency ward for observation and/or treatment that would not have been appropriate in the physician's office or outpatient setting. When in doubt as to whether 'hospitalization' occurred or was necessary, the AE should be considered serious.
- AEs requiring hospitalization should be considered SAEs. Hospitalization planned prior to study enrollment (eg, for elective surgery or routine clinical procedures) that are not the result of AE (e.g., elective surgery for a pre-existing condition that has not worsened) need not be considered AEs or SAEs. If anything untoward is reported during the procedure, that occurrence must be reported as an AE, either 'serious' or 'nonserious' according to seriousness criteria described above.
- Disability/Incapacity
 - An AE is disabling or incapacitating if it results in substantial and/or permanent disruption of the subject's ability to carry out normal life functions.
- Congenital anomaly/birth defect not present at screening
- Important Medical Events that may not result in death, be immediately life-threatening, or require hospitalization may be considered serious when, based upon appropriate medical judgment, they may jeopardize the patient or subject and may require medical or surgical intervention to prevent one of the criteria listed in the definition. Examples of such events are:
 - Intensive treatment in an emergency room or at home for allergic bronchospasm
 - Blood dyscrasias that do not result in inpatient hospitalization
 - Development of drug dependency or drug abuse

8.4.3 Classification of an Adverse Event

8.4.3.1 Severity of Event

The Investigators will provide an assessment of the severity of each AE by recording a severity rating on the appropriate AE reporting page of the participant's CRF. The severity of all AEs will be graded using the Common Terminology Criteria for Adverse Events (CTCAE) version 5.0.

8.4.3.2 Relationship to Study Intervention

All adverse events (AEs) must have their relationship to study intervention assessed by the investigator who examines and evaluates the subject based on temporal relationship and their clinical judgment and the information provided in the Reference Safety Information. Treatment-

related conditions must be distinguished from disease-related conditions. The degree of certainty about causality will be graded using the categories below. In a clinical trial, the study product must always be suspect.

- **Related:** The available evidence suggests there is a reasonable possibility that the study drug caused the adverse. For example, a temporal relationship exists between the AE onset and administration of the study drug that cannot be readily explained by the subject's clinical state, concurrent disease or concomitant therapies. 'Reasonable possibility' means there is evidence to suggest a causal relationship between the drug and the AE.
- **Not related:** The available evidence suggests an unrelated AE is one for which there is not a reasonable possibility that the drug caused the AE. The adverse event is most likely related to factors other than the administration of the study drug. Such other factors may include the underlying disease state, comorbidities, an intercurrent illness, concomitant medication(s) or procedures.

A causality assessment should include, for example, assessment of temporal relationship, physiologic plausibility, dechallenge/rechallenge information, association with (or lack of association with) underlying disease, and presence (or absence) of a more likely cause. The PI may change the causality assessment at any time based on new accumulated information.

Note: The Investigator's assessment of causality for individual AEs is part of the study documentation process and will be recorded in the CRF and SAE form, if applicable. AEs recorded without the Investigator's assessment of the relationship to study drug will be followed up until causality is assigned.

8.4.3.3 Expectedness

An adverse event or suspected adverse reaction is considered "unexpected" if it is not listed in the investigator brochure or is not listed at the specificity or severity that has been observed or is not consistent with the risk information described in the general investigational plan. The sponsor will evaluate the available information and decide whether there is a reasonable possibility that the drug caused the adverse event and, therefore, that the event meets the definition of a suspected adverse reaction. The suspected adverse reaction will then be reported expeditiously in an IND safety report if it also meets the definitions of serious and unexpected (21 CFR 312.32(c)(1)(i)).

8.4.4 Time Period and Frequency for Event Assessment and Follow-Up

The occurrence of an adverse event (AE) or serious adverse event (SAE) may come to the attention of study personnel during study visits and interviews of a subject presenting for medical care, or upon review by a study monitor.

All AEs including local and systemic reactions not meeting the criteria for SAEs will be captured on the appropriate case report form (CRF). Information to be collected includes event description, time of onset, clinician's assessment of severity, relationship to study product (assessed only by those with the training and authority to make a diagnosis), and time of resolution/stabilization of the event. All AEs occurring while on study must be documented appropriately regardless of relationship. All AEs will be followed to adequate resolution.

Any medical condition that is present at the time that the subject is screened will be considered as baseline, recorded as patient medical history, and not recorded as an AE. However, if the subject's condition deteriorates at any time during the study, it will be recorded as an AE.

Changes in the severity of an AE will be documented to allow an assessment of the duration of the event at each level of severity to be performed. AEs characterized as intermittent require documentation of onset and duration of each episode. At each study visit, the investigator will inquire about the occurrence of AE/SAEs since the last visit. The study team will record all reportable events with start dates occurring any time after informed consent is obtained until 4 weeks after the last burosomab dose. Events will be followed for outcome information until resolution or stabilization.

8.4.5 Adverse Event Reporting

Any untoward medical occurrences or unfavorable and unintended signs, symptoms, or diseases that occur in the pretreatment, treatment, or posttreatment period are to be considered AEs (and SAEs if appropriate), and consequently recorded and reported as such.

Subjects are to be queried regarding any AEs or SAEs at the time of each vital sign assessment, as well as at each visit, according to the Schedule of Activities (Section 1.3). Subjects will be asked to volunteer information with a nonleading question such as, "How do you feel?" Study center personnel will then record all pertinent information in the subject's CRF.

All AEs and SAEs reported by the subject (or subject's legal representative) or observed or otherwise identified by the investigator (or other study center personnel) at a defined study visit or during any communication with the subject (or subject's legal representative) occurring outside a defined study visit (from the time the subject signs the ICF to 30 ± 7 days after the last dose of burosomab) must be documented.

All AEs must be recorded on the appropriate AE reporting page of the subject's CRF whether or not they are considered causally related to the burosomab.

For every AE, the investigator must:

- Provide an assessment of the severity, causal relationship to burosomab, and seriousness of the event (i.e., whether it is a SAE)
- Document all actions taken with regard to burosomab
- Detail any other treatment measures taken for the AE
- Document resolution of the AE (with or without sequelae); ongoing; or lost to follow-up.

8.4.6 Serious Adverse Event Reporting

In consultation with the PI, a trained member of the study team will be responsible for conducting an evaluation of all adverse events and shall report the results of such evaluation to the NIH Institutional Review Board (IRB) as per [Policy 801](#).

All SAEs will be reported to the NIDCR Office of the Clinical Director within 7 days of investigator awareness. The study sponsor will be responsible for notifying the Food and Drug Administration (FDA) of any unexpected fatal or life-threatening suspected adverse reaction as soon as possible, but in no case later than 7 calendar days after the sponsor's initial receipt of the information. In addition, the sponsor must notify FDA and all participating investigators in an Investigational New Drug (IND) safety report of potential serious risks, from clinical trials or any

other source, as soon as possible, but in no case later than 15 calendar days after the sponsor determines that the information qualifies for reporting.

8.4.7 Reporting of Serious Adverse Events to Kyowa Kirin Pharmacovigilance

In addition to any IND reporting requirements to the FDA, all serious adverse events (regardless of causality) must be reported to Kyowa Kirin via a MedWatch 3500A Form or equivalent form within 24 hours of knowledge of the event to: [contact].

8.4.8 NIH Intramural IRB Reporting of IND Safety Reports

Only IND Safety Reports that meet the definition of an unanticipated problem or is new information that might affect the willingness of subjects on the NIH study to enroll or remain in the study will need to be reported to the NIH Intramural IRB.

8.4.9 Events of Special Interest

Not applicable

8.4.10 Reporting of Pregnancy and other Special Situations

Pregnancies in subjects or partners must be reported within 24 hours of knowledge of investigator awareness to Kyowa Kirin at [contact]. The reporting period for pregnancies is the period from the signing of the ICF until 30 ± 7 days after the last dose of burosumab. Reported pregnancy of a subject or a subject's partner, while participating in the study, will be monitored for the full duration and/or followed until the outcome of the pregnancy is known. In the event of a pregnancy in the partner of a subject, the Investigator should make every effort to obtain the female partner's consent for release of protected health information. Pregnancies in subjects or partners will be reported to the NIDCR Office of the Clinical Director within 7 days of investigator awareness.

In addition, the following other special situations arising with the use of burosumab whether or not associated with an adverse event must be reported to Kyowa Kirin [contact] within 24 hours of knowledge of the event:

- Overdose, defined as a known deliberate or accidental administration of investigational drug, to or by a study subject, at a dose above that which is assigned to that individual subject according to the study protocol
- Suspected or confirmed transmission of infectious agents via product (must always itself be considered an SAE)

8.4.11 Safety Updates from Kyowa Kirin to NIH

During the course of the study, Kyowa Kirin will report to the investigator any safety related major issues (issues potentially leading to major impact on the risk-benefit balance of a product/compound and/or on patients' or public health including health hazard or lawsuits, which may require regulatory actions such as product recall, product withdrawals, removal of approved indications, failure to obtain product registration renewal due to safety reason, termination of studies, label changes, or prompt communication to patients and healthcare professionals) or any new information about the study product, that does not fall within the definition of an IND safety report, that poses a significant health or safety risk to study

participants or affects the willingness of study participants to continue their participation in the study.

8.5 Unanticipated Problems

8.5.1 Definition of Unanticipated Problems (UP)

Any incident, experience, or outcome that meets all of the following criteria:

- Unexpected in terms of nature, severity, or frequency given (a) the research procedures that are described in the protocol-related documents, such as the Institutional Review Board (IRB)-approved research protocol and informed consent document; and (b) the characteristics of the participant population being studied; and
- Related or possibly related to participation in the research (“possibly related” means there is a reasonable possibility that the incident, experience, or outcome may have been caused by the procedures involved in the research); and
- Suggests that the research places participants or others (which many include research staff, family members or other individuals not directly participating in the research) at a greater risk of harm (including physical, psychological, economic, or social harm) than was previously known or expected.

8.5.2 Unanticipated Problem Reporting

The investigator will report unanticipated problems (UPs) to the NIH Institutional Review Board (IRB) as per [Policy 801](#).

9 STATISTICAL CONSIDERATIONS

9.1 Statistical Hypothesis

This single-arm open-label trial is to gather preliminary information on the effectiveness and safety of burosumab in FD patients. Estimates for the primary and secondary endpoints will be provided.

- Primary Endpoint: The proportion of subjects achieving serum phosphate levels within the target range (Z-score -1 to +2) at Week 48.
- Secondary Endpoints:
 - Proportion of subjects achieving serum phosphate levels within the target range (Z-score -1 to +2) at Week 24
 - Adverse events and clinical safety laboratory tests for up to 4 weeks following the final burosumab dose (48 weeks for adults, 50 weeks for children).
 - Proportion of subjects achieving mean serum phosphate levels above the target range (Z-score >+2), as averaged across dose cycles between Baseline and Week 48
 - Change and percent change from baseline to post-baseline visits in serum phosphate, serum 1,25(OH)2D, ratio of renal tubular maximum reabsorption rate of phosphate to glomerular filtration rate (TmP/GFR)
 - Change in FD lesion activity using ¹⁸F-NaF PET/CT total lesion activity from baseline to 48 weeks

- Change and percent change in serum bone turnover markers, including procollagen 1 N-terminal propeptide (P1NP), beta crosslaps C-telopeptides (CTX), osteocalcin, and bone-specific alkaline phosphatase from baseline to 48 weeks
- Change in FD lesion histology and cell proliferation as assessed by minimally invasive bone biopsies from baseline to 48 weeks (adults with capacity to consent only) from baseline to 48 weeks
- Change from baseline to 48 weeks in muscle strength, range-of-motion, and walking speed (9-minute walk)
- Change from baseline to 48 weeks in patient reported outcomes measures: SF36 (adults), SF10 (children), Brief Pain Inventory (adults and children), Brief Fatigue Inventory (adults and children)

9.2 Sample Size Determination

For the primary endpoint, the proportion of subjects achieving serum phosphate levels within the target range (Z-score -1 to +2) at Week 48, we will use the Clopper-Pearson exact method to calculate the confidence interval of the proportion. Table 7 below shows different widths achieved assuming different true proportions. Calculations were done using the statistical software PASS (Power Analysis and Sample Size, NCSS). With a sample size of 10, we will be able to provide a two-sided 95% confidence interval (CI) with a width of no more than 0.44 when the true proportion is 0.9 (which we expect to be most likely). A total of 15 subjects will be recruited to ensure that 10 of them will have at least 48 weeks of follow-up time.

Table 7. Confidence interval widths achieved assuming different true proportions (N=10)

True proportion	0.5	0.6	0.7	0.8	0.9	0.95
CI width	0.63	0.62	0.59	0.53	0.44	0.38
95% CI	(0.19, 0.81)	(0.26, 0.88)	(0.35, 0.93)	(0.44, 0.97)	(0.55, 1)	(0.62, 1)

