4 STUDY DESIGN

4.1 Overall Design

This is a single center, single-arm, open-label study to evaluate the efficacy and safety of burosumab treatment for FGF23-mediated hypophosphatemia in patients with FD/MAS. All subjects will be co-enrolled and screened through Screening and Natural History protocol 98-D-0145, a longstanding natural history study of FD/MAS protocol 98-D-0145. Up to 15 subjects will be enrolled, with the goal of a minimum 10 subjects receiving 48 weeks of burosumab treatment with week 50 for a final adverse event review. Research activity will be conducted at the NIH Clinical Center, with outpatient laboratory monitoring and burosumab self- and/or caregiver administration between NIH visits. Study subjects will be evaluated weekly on weeks 1-4 and then every two weeks for weeks 6-50.

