9.3 Populations for Analyses

- Safety Analysis Dataset: This will include participants who took at least one dose of burosomab.
- Efficacy Analysis Dataset: This will include all participants who received at least one dose of burosomab and have sufficient post-baseline assessment data to enable analyses of study endpoints. For the proportions evaluated at week 48 (the primary endpoint and some secondary endpoints), subjects who have completed 48 weeks of therapy and returned for the week 48 assessment will be included in the analysis.

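### Section 9.2 gives 0.44 as the maximum CI width at a true proportion of 0.9, but it is the width when 9 of 10 are observed in range; Table 7's 0.95 interval cannot occur with 10 subjects

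*Combined protocol and SAP*

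**What the plan says.** Section 9.2 (Sample Size Determination) rests the sample size on the precision of the primary endpoint, the proportion in the target phosphate range at Week 48. On method it states: "we will use the Clopper-Pearson exact method to calculate the confidence interval of the proportion". It introduces its table with "Table 7 below shows different widths achieved assuming different true proportions", and the row of Table 7 carries the same true-proportion label for N=10. The central claim is that with 10 subjects the trial will be "able to provide a two-sided 95% confidence interval (CI) with a width of no more than 0.44 when the true proportion is 0.9", and 0.9 is named as the likeliest value.

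Table 7 gives widths of 0.63, 0.62, 0.59, 0.53, 0.44 and 0.38 for proportions 0.5, 0.6, 0.7, 0.8, 0.9 and 0.95. The interval is (0.55, 1) at 0.9 and (0.62, 1) at 0.95.

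On numbers, Section 9.2 says "A total of 15 subjects will be recruited to ensure that 10 of them will have at least 48 weeks of follow-up time", while Section 4.1 describes enrolment of up to 15 "with the goal of a minimum 10 subjects receiving 48 weeks of burosumab treatment". Section 9.3 sets the Week 48 analysis set: "subjects who have completed 48 weeks of therapy and returned for the week 48 assessment will be included in the analysis".

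**The concern.** The width of an exact binomial interval is fixed by the number of successes observed. For a given true proportion that number is random, so the width is random too. A single width tied to a true proportion can be an average or a quantile. It can be an upper limit only if it is the largest width that can occur, and Table 7 itself lists larger widths for the same N.

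Section 9.1 frames the trial as estimation, with no null value and no power, so this sentence and table are the only quantitative case for the sample size. As worded, they tell the reader that an interval no wider than 0.44 is assured in the scenario the plan thinks likeliest. The design does not have that property. The 0.95 column has a second problem: 0.95 × 10 = 9.5, which is not a possible count.

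**Working it through.** **Inputs.** From Section 9.2: Clopper-Pearson method, two-sided 95% (0.025 per tail), n = 10, proportions as in Table 7. From Sections 4.1 and 9.3: up to 15 enrolled, with all Week 48 completers analysed.

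**Formulas.** For x in range out of n:
- lower limit = the 0.025 quantile of Beta(x, n − x + 1)
- upper limit = the 0.975 quantile of Beta(x + 1, n − x)
- at x = n, the lower limit is 0.025^(1/n) and the upper limit is 1

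**Step 1: reproduce Table 7.** Enter x = 10 × the tabulated proportion as an observed count. For comparison, the last column averages the width over Binomial(10, p), with p as the true proportion.

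| Proportion | x used | 95% CI | Width | Table 7 width | Expected width if p is the true proportion |
|---|---|---|---|---|---|
| 0.5 | 5 | 0.187–0.813 | 0.626 | 0.63 | 0.600 |
| 0.6 | 6 | 0.262–0.878 | 0.616 | 0.62 | 0.590 |
| 0.7 | 7 | 0.348–0.933 | 0.586 | 0.59 | 0.559 |
| 0.8 | 8 | 0.444–0.975 | 0.531 | 0.53 | 0.505 |
| 0.9 | 9 | 0.555–0.997 | 0.4425 | 0.44 | 0.423 |
| 0.95 | 9.5 | 0.619–1.000 | 0.381 | 0.38 | 0.371 |

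Every column matches the observed-proportion reading, and none matches the expected width. Other methods do not give (0.55, 1) at 9/10: Wilson 0.60–0.98, Jeffreys 0.62–0.99, Agresti-Coull 0.57–1, Wald 0.71–1. So the table does use Clopper-Pearson, with the tabulated value treated as observed.

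**Step 2: the 0.95 column.** The widths for x = 0 to 10 are 0.3085, 0.4425, 0.5309, 0.5857, 0.6161, 0.6258, 0.6161, 0.5857, 0.5309, 0.4425 and 0.3085. No whole-number count gives 0.38 or (0.62, 1). The possible results at that end are 9/10 (0.555–0.997, width 0.44) and 10/10. For 10/10 the lower limit is 0.025^(1/10) = 0.692, so the interval is 0.692–1.00 with width 0.31.

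**Step 3: distribution of the width at a true proportion of 0.9, n = 10.**
- 10/10: 0.9^10 = 0.349, width 0.31
- 9/10: 10 × 0.9^9 × 0.1 = 0.387, width 0.44
- 8/10: 45 × 0.9^8 × 0.1^2 = 0.194, width 0.53
- 7 or fewer: 0.070 in total, width 0.59 to 0.63 for counts 3 to 7; counts 0 to 2 have negligible probability

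P(8 or fewer) = 1 − 0.349 − 0.387 = 0.264. This counts 0.4425 as meeting a limit of 0.44. The narrow intervals at 0 or 1 of 10 contribute less than 1e-8.

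Expected width = 0.349 × 0.3085 + 0.387 × 0.4425 + 0.194 × 0.5309 + the terms for 7 or fewer (about 0.042) = 0.423. The largest possible width at n = 10 is 0.626, at 5/10.

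**Step 4: other numbers of completers, true proportion 0.9.**

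| n | Expected width | P(rounded width > 0.44) |
|---|---|---|
| 9 | 0.448 | 61% |
| 10 | 0.423 | 26% |
| 11 | 0.402 | 30% |
| 12 | 0.384 | 34% |
| 13 | 0.368 | 13% |
| 14 | 0.353 | 16% |
| 15 | 0.340 | 6% |

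The limit is not guaranteed at any of these sizes. The chance does not fall steadily with n because the counts are discrete.

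**The case against.** The strongest defence is that Table 7 is a planning illustration. An anticipated proportion is put into the interval formula, the plan says PASS was used, and no entry is miscalculated. On that view the 0.95 column is an interpolated planning value, not a forecast of a result. Average precision is also not overstated: every expected width is below the tabulated one, and the table openly shows widths up to 0.63. Nothing downstream uses 0.44. Section 9.4.2 plans only the exact interval, there is no success rule, and Section 4.2 describes an extremely small target population.

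Most of this stands, and it keeps the point minor. It does not rescue the text. Neither the row label nor the sentence says that the entries are conditional on an observed proportion, and wording the width as a limit is wrong on any reading in which 0.9 is the true value.

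Two narrower objections also carry weight. Section 9.2 makes its claim for n = 10 only, so the figures for other n are supporting context and not a contradiction of the text. The contrast between ensuring 10 completers (Section 9.2) and aiming for them (Section 4.1) is a difference of wording about the same intention, and the main point does not depend on it.

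**Conclusion.** The point holds as a minor error of description. The arithmetic behind Table 7 is right, but its label and the sentence drawn from it are wrong. With exactly 10 completers, independent outcomes and a true proportion of 0.9, the stated limit is met with probability 0.736 and missed with probability 0.264. When it is missed, the width is about 0.53 or more, against an expected width of 0.42. The 0.95 interval is unattainable with 10 subjects whatever the true proportion. The planned primary analysis, the enrolment target and the eventual estimate are unaffected. What changes is how the precision of the design is described to a reader judging whether 10 completers are enough.

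**What to change.** In Section 9.2:

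1. Relabel the first row of Table 7 as the observed proportion (x/10), and change the table title and lead-in sentence to match.
2. Replace the 0.95 column with 10/10: 95% CI (0.69, 1.00), width 0.31.
3. Replace the sentence on the 0.44 width with:

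> If 9 of 10 subjects are in range, the 95% CI is 0.555 to 0.997 (width 0.44). If the true proportion is 0.9 and 10 subjects complete, the expected width is 0.42, with a 26% chance of a width of about 0.53 or more.

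4. Optionally, describe 10 completers as a goal, in line with Section 4.1.

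The cost is rewording one paragraph and one table. No extra subjects are needed and the analysis does not change. The plan gives up a stated upper limit and gains a correct average that is slightly narrower (0.42 against 0.44).
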